4.2. SAFETY ENDPOINTS

Safety endpoints are as follows:

- Incidence of treatment-emergent drug/device-related adverse events
- Changes from Baseline to Month 2/Study Termination in clinical laboratory and vital signs*

* Changes from Baseline to Month 2 and Month 4 will be summarized. In the absence of data at the relevant visit early termination data may be used if collected within the visit window (see Section 6.4).

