3.2.2. Safety Endpoints

Safety endpoints are as follows:

- Incidence of treatment-emergent drug/device-related adverse events
- Changes from Baseline to Month 2/Early Termination in clinical laboratory, physical exam findings, and vital signs

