6.6. Physical Examinations

A full physical exam (PE) will consist of assessments of the following: skin, ears, nose, throat, head, eyes, lungs/chest, heart, abdomen, musculoskeletal, extremities, neurologic, and lymphatic.

A brief physical exam includes all the body systems of the full PE, except for eyes, musculoskeletal, and neurologic.

All physical exam findings must be assessed as not clinically significant or clinically significant by the Investigator and recorded in the source document and eCRF. Clinically significant changes noted in PE findings should be recorded as an AE.

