7.1. Definition of a Treatment-Emergent Adverse Event

An AE is any untoward medical occurrence associated with the use of a drug in humans, whether or not considered drug related. All AEs that occur after the time of treatment with the investigational product will be considered a Treatment Emergent AE (TEAE).

A TEAE can be any unfavorable and unintended sign (e.g., an abnormal laboratory finding), symptom, or disease temporally associated with the use of a drug, without any judgment about causality.

A TEAE **does** include any:

- Exacerbation of a pre-existing illness.
- Increase in frequency or intensity of a pre-existing episodic event or condition.
- Condition detected or diagnosed after study drug administration even though it may have been present prior to the start of the study.

- Continuous persistent disease or symptoms present at baseline that worsen following the start of the study.
- Events considered by the investigator to be related to study-mandated procedures.
- Abnormal assessments (e.g., change in physical examination), if they represent a clinically relevant finding, that were not present at Baseline or worsened during the course of the study.
- Laboratory test abnormalities, if they represent a clinically relevant finding, symptomatic or not, which were not present at Baseline or worsened during the course of the study.

A TEAE **does not** include a/an:

- Medical or surgical procedure (e.g., surgery, endoscopy, tooth extraction, transfusion); the condition that leads to the procedure is an AE.
- Situations where an untoward medical occurrence has not occurred (e.g., hospitalization for cosmetic elective surgery, social and/or convenience admissions).
- Overdose of either study drug or concurrent medication without any signs or symptoms.
- Hospitalization for elective treatment of a pre-existing condition that did not worsen during the study is not considered an AE.

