8.4. PHYSICAL EXAMINATION

All abnormal findings at Baseline will be recorded on the Medical History/Concomitant Diagnoses page (or equivalent) of the case report form. New abnormal findings or a worsening of baseline conditions detected at follow-up physical examinations will be recorded as AEs on the eCRF.

Physical examination data will be listed.

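### SAP v2.0 leaves physical exam findings out of the safety endpoint without explanation and plans only a listing of them

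*SAP*

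**What the plan says.** Protocol 3.2.2, and the synopsis in the same words, name as a safety endpoint "Changes from Baseline to Month 2/Early Termination in clinical laboratory, physical exam findings, and vital signs". SAP 4.2 restates it as "Changes from Baseline to Month 2/Study Termination in clinical laboratory and vital signs".

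SAP 8.2 and 8.3 plan observed values and changes from baseline at Months 2 and 4 for laboratory data and vital signs, plus a last on-treatment summary. For exams, SAP 8.4 ends with "Physical examination data will be listed" and plans nothing further.

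On AE recording, SAP 8.4 says: "New abnormal findings or a worsening of baseline conditions detected at follow-up physical examinations will be recorded as AEs on the eCRF". Protocol 6.6 is narrower: "Clinically significant changes noted in PE findings should be recorded as an AE". The same protocol section has every finding graded: "All physical exam findings must be assessed as not clinically significant or clinically significant by the Investigator". These grades go into the source document and the eCRF.

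**The concern.** A protocol safety endpoint with three components becomes one with two in the SAP, and the SAP does not record this as a change. The primary objective is long-term safety and tolerability, so a missing safety component invites a question when the final report is read against the protocol.

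The AE sentence in SAP 8.4 makes the gap look smaller than it is. Taken at face value, it means that every new or worsened exam finding is counted in the AE tables. Under the protocol's recording rule, only some of them are.

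**Working it through.** No formula applies and the plan gives no figure to reproduce. The check compares the texts.

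**1. Endpoint components and planned outputs**

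| Component | Protocol 3.2.2 and synopsis | SAP 4.2 | Planned output in SAP v2.0 |
|---|---|---|---|
| Laboratory | yes | yes | change summaries and shift tables at Months 2 and 4 (8.2) |
| Vital signs | yes | yes | change summaries at Months 2 and 4 (8.3) |
| Physical exam findings | yes | no | listing only (8.4) |

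Three components become two: 3 − 1 = 2. Exam findings have one listing and no summary, change or shift table.

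**2. Which findings reach a table**

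- A change rated clinically significant is recorded as an AE under protocol 6.6. It is then counted in the TEAE tables of SAP 8.1 by system organ class and preferred term. That is an AE count, not a change from baseline in exam findings.
- A new finding rated not clinically significant need not be recorded as an AE. The exam item in the TEAE definition (protocol 7.1) has the same limit: "Abnormal assessments (e.g., change in physical examination), if they represent a clinically relevant finding". Such a finding appears in the exam listing and in no summary table.

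The unqualified sentence in SAP 8.4 is therefore broader than protocol 6.6 and the exam item in 7.1.

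**3. What the exam schedule can support**

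The full exam in protocol 6.6 covers 13 items: skin, ears, nose, throat, head, eyes, lungs/chest, heart, abdomen, musculoskeletal, extremities, neurologic and lymphatic. For the short form, "A brief physical exam includes all the body systems of the full PE, except for eyes, musculoskeletal, and neurologic". That leaves 13 − 3 = 10.

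Protocol Appendix 1 schedules these exams:

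- Screening: full (13)
- Baseline and Month 2: brief (10)
- Month 4, every 12 months thereafter, and the Termination Visit: full (13)

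Baseline to Month 2 can thus be compared for 10 systems. Eyes, musculoskeletal and neurologic have no scheduled Month 2 rating. All 13 can be compared from Screening to Month 4 and from Screening to the Termination Visit.

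**4. Whether the omission is explained elsewhere**

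SAP 2 says that data through Month 2 were summarised in a clinical study report under an initial SAP, which is not among the documents. Where SAP v2.0 relies on or repeats that reporting, it says so: for pharmacokinetics (4.3), demographics (7.2), medical history (7.3) and prior medications (7.4). It says nothing of the kind for exams, and it summarises the Month 2 laboratory and vital-sign changes again.

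**The case against.** The strongest defence is that the SAP follows the protocol's own analysis text. Protocol 8.7 lists exposure, AEs, device effects, laboratory data and vital signs for descriptive summary, and not exams. The synopsis's statistical considerations are likewise silent on exams. This stands in part, because the mismatch begins inside the protocol. But protocol section 8 describes itself as an overview and says that the final analyses may go beyond it. A short list there does not remove an endpoint defined in 3.2.2.

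It is also fair that the consequence is small. The study is descriptive, with no formal hypothesis test. What stays outside the tables is mainly what investigators judged not clinically significant, and that is still listed. For worsened findings the gap is less clear than for new ones: protocol 7.1 also counts exacerbation of a pre-existing illness, and worsening of persistent baseline disease or symptoms, without a clinical-significance qualifier.

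Three stronger readings are tempting, and the documents do not support them.

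- A reader might infer that the component is never reported. The data are listed, clinically significant changes enter the TEAE tables, and the Month 2 study report may have summarised it.
- A reader might infer that the SAP plans only a listing because it believes the AE tables capture everything. SAP 8.4 states a recording rule but never gives it as the reason.
- A reader might multiply the 113 subjects with a Month 2 visit (SAP 3.3) by 10 systems and speak of 1,130 ratings left unsummarised. The 113 counts visits, not exams done, and the documents do not show that the eCRF holds a rating for each body system.

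The missing Month 2 rating for three systems comes from the protocol's schedule and is not an SAP error. Early terminators have a full exam, and SAP 6.2.1 allows a screening value to stand in for a missing baseline. It matters here only because it determines what a table can show.

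**Conclusion.** The point holds as a gap in SAP v2.0. Physical exam findings are one of three components of a protocol safety endpoint. They are omitted from SAP 4.2 without explanation and are not summarised in the final analysis. The AE sentence in 8.4 lacks the protocol's clinical-significance qualifier, so new findings rated not clinically significant appear in no summary table.

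The size is one component of three. The number of findings affected cannot be derived from the documents. The conclusion concerns the final reporting under SAP v2.0 and assumes that sites followed protocol 6.6 when deciding what to record as an AE. Whether the Month 2 report covered the component is unknown. Even if it did, a report ending at Month 2 would not cover Month 4, to which the SAP extends the other two components. The correction is worth making, but the consequence is minor: the primary endpoint and the sample size do not change.

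**What to change.** 1. In SAP 4.2, restore physical exam findings to the endpoint.
2. In SAP 8.4, add one descriptive table of new or worsened findings by body system and clinical significance, as far as the eCRF records them. Use Baseline to Month 2 for the 10 brief-exam systems, and Screening to Month 4 and to the Termination Visit for all 13.
3. Reword the AE sentence in SAP 8.4 to match protocol 6.6: clinically significant changes are recorded as AEs.
4. If the Month 2 study report already summarised the component, cite it in 8.4. If the sponsor prefers not to add the table, state and justify the omission as a departure from protocol 3.2.2.

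The cost is SAP wording and one extra table, subject to a check of how the eCRF stores exam findings. SAP 2 allows amendments before database lock. After lock, the same section provides for documenting additional analyses or deviations in the study report.

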4.3. PHARMACOKINETIC ENDPOINTS

The details for these endpoints can be found in the protocol and the PK SAP. As PK data have already been reported no further details will be provided in this SAP.

4.4. EXPLORATORY ENDPOINTS

For all patients:

- Change from Baseline to Week 2 and Months 1, 2, 4 and every 4 months thereafter in 6MWD
- Change from Baseline to Week 2 and Months 1, 2, 4 and every 4 months thereafter in NYHA Functional Class status
- Change from Baseline to Week 2 and Months 1, 2, 4 and every 4 months thereafter in NT-proBNP levels
- Change from Baseline to Month 2, Month 4, and every 12 months thereafter in the Minnesota Living with Heart Failure (MLWHF) Quality of Life Questionnaire
- Time to and reason for discontinuation of LIQ861

For transitioning from Tyvaso only:

- Proportion of patients maintaining a sustained treatment transition through the end of Month 2. Sustained treatment transition is defined as meeting the following conditions: 1) current treatment with LIQ861 through at least 2 months beyond transition from Tyvaso, 2) no interruptions to study treatment totaling more than 7 days prior to the end of Month 2, and 3) no treatment with any prostacyclin or prostacyclin analogs apart from administration of LIQ861.
- Comparison of LIQ861 dose achieved at sustained treatment to previous Tyvaso dose.
- Patient satisfaction with the LIQ861 DPI compared to the inhalation device from which they are transitioning from using a simple questionnaire to assess device preference.

5. ANALYSIS POPULATIONS

As data through Month 2 have already been reported for Study LTI301 the participants have already been classified for each population. The same classifications will be used for these analyses.

5.1. SCREENED POPULATION

The Screened Population includes all subjects who signed the informed consent.

This population includes 146 subjects.

5.2. SAFETY POPULATION

The Safety Population includes all subjects who received at least 1 inhalation of LIQ861.

This population includes 121 subjects (55 Transition and 66 Add-On).

5.3. EFFICACY POPULATION

The Efficacy Population includes all subjects who received at least 1 inhalation of LIQ861 and provided at least 1 post-Baseline efficacy assessment.

This population includes 120 subjects (55 Transition and 65 Add-On).

5.4. MODIFIED INTENT TO TREAT POPULATION

The Modified Intent-to-Treat (mITT) Population includes all subjects who received at least 1 inhalation of LIQ861 and were identified as WHO Group 1, based upon adjudication by a panel of PAH experts (refer to Study LTI-301 Adjudication Committee Charter).

This population includes 106 subjects (46 Transition and 60 Add-On).

6. GENERAL ASPECTS FOR STATISTICAL ANALYSIS

6.1. GENERAL METHODS

Subjects differ by treatment history prior to entry to Study LTI-301 - the two groups will be referred to as the Transition and Add-On Groups. For all summary tables data will be presented for all subjects (Overall) and by group.

Continuous variables will be summarized using the number of non-missing observations (n), mean, standard deviation (SD), standard error (SE), median, minimum and maximum. Categorical variables will be summarized using frequencies and percentages.

Categorical shift tables will include marginal totals.

Unless otherwise specified, the estimated mean and median for a set of values should be printed out to 1 more decimal place than the original values, and SD and SE should be printed out to 2 more decimal places than the original values. The minimum and maximum should report the same number of decimal places as the original values.

Percentages will be displayed with 1 decimal place; except percentages will not be presented when the count is zero and 100% will be presented as an integer. The number of subjects in the analysis population will be the denominator.

Unless stated otherwise, baseline will be taken as the last available non-missing assessment prior to study drug administration (Day 1).

In by-visit summary tables, the baseline will be summarized using all available data, but also for each visit using only the baseline data from subjects with available data at the visit; hence the mean change from baseline will equal the mean visit value – mean baseline value.

Throughout this document ‘change from baseline’ refers to the actual change from baseline (i.e. visit value – baseline value).

All data will be listed separately for each group. Data listings will present study days in addition to dates, where study day is derived as (assessment date – first day of dosing + 1).

Since there is no formal hypothesis testing, no adjustment for multiplicity will be made for inferential statistical comparisons within or between groups.

Programming of analyses, tables and listings will be performed using R Version 3.4.0 or higher (R Foundation for Statistical Computing, Vienna, Austria) or SAS® Version 9.3 or higher (Cary, North Carolina, US).

6.2. MISSING DATA

All possible efforts will be made to minimize missing data. No imputation of missing data will be performed unless specifically mentioned.

The original data will always be presented in the listings.

6.2.1. MISSING BASELINE

Unless specified otherwise, screen values or pre-dose unscheduled measurements may be used as a baseline value in the event of missing Day 1 pre-dose measurements.

6.2.2. ADVERSE EVENT CLASSIFICATIONS

AEs with missing classifications will be assumed to be the following:

- missing causality will be taken as treatment related
- missing seriousness will be taken as serious
- missing severity will be taken as severe

6.2.3. PARTIAL OR MISSING DATES

For missing or partial dates for adverse events and medications the following rules will be applied to impute the date:

If the start date is incomplete, then it will be imputed as follows:

- If the start date is completely missing, the start date will be equal to the first dose date (Day 1). However, if the stop date is not missing and is before the first dose date, then the stop date will be used instead.
- If the start day is missing: check if month is same as month of first dose date of study treatment. If yes, impute to first dose date of study treatment; else impute first day of the month. However, if the stop date is not missing, is the same month as the start day and is before the first dose of study treatment, then the stop date will be used instead.
- If the start day and month are missing: check if year is same as the year of the first dose date of study treatment. If yes, impute to first dose date of study treatment; else impute to first day of the first month (January). However, if the stop date is not missing, is the same year as the start day and is before the date of the first dose of study treatment, then the stop date will be used instead.

If the stop date is incomplete, then it will be imputed as follows:

- If the stop date is completely missing and the medication/event is not ongoing, the stop date will be imputed as the date of study withdrawal.
- If the stop day is missing, the last day of the month will be used. If resulted imputed stop date is after the date of study withdrawal, then the date of study withdrawal will be used.
- If the stop day and month are missing, then the last day of the last month (31st December) will be used. If resulted imputed stop date is after the date of study withdrawal, then the date of study withdrawal will be used.

The original reported partial dates will be provided in listings, but study days and derived variables (e.g. durations) will be use the imputed dates.

6.2.4. LABORATORY VALUES

If laboratory parameters are reported as out of assay range, e.g. $< x$ or $> y$ the limit of quantification will be used in the calculation of summary statistics. However, the listing will present the data as originally reported (e.g. $< x$).

6.2.5. SUMMARY TABLE PRESENTATIONS

In summaries for continuous data, the number of missing values will be presented. The missing count will not include subjects who have discontinued at earlier visits or not had the potential to reach the visit (i.e. subject transitioned to extension study prior to reaching the visit).

In summaries for categorical data the following categories will be included:

- No potential to reach the visit
- Withdrew prior to the visit
- Missing

6.3. SUBGROUPS

The following subgroups will be used:

- Age (< 65 years of age, \geq 65 years of age)
- Age (<75 years of age, \geq 75 years of age) – NT-proBNP only
- Sex (Female, Male)
- Race (Asian, Black, White, Other)
- Number of PAH specific medications at baseline (none, 1, 2)
- Duration since diagnosis (\leq 5 years, $>$ 5 years)

6.4. VISIT WINDOWS

Data will be assigned to visits using windowing (see table below). If more than one assessment (including the early termination or unscheduled assessments) falls within the same defined window, the assessment closest to the target day with non-missing data will be considered for analysis; however, with the exception of laboratory and vital sign data, the visit must be within 7 days of the final dose of study treatment. For laboratory and vital sign data the assessment must be no more than 1 day after the final dose of study treatment. If two qualifying assessment dates are at the same distance from the target day, the latest assessment with non-missing data will be taken for analysis.

Visit	Target Day	Analysis Window	Interval
Baseline ^a	1 ^b	Day -30 to Day 1	
Week 2	14	2 -22	21
Month 1	30	23 – 45	23
Month 2	60	46 – 90	45

Visit	Target Day	Analysis Window	Interval
Month 4	120	91 – 150	60
Month 8	240	211 – 270	60
Month 12	360	331 – 390	60
Month 16	480	451 – 510	60
Month m	30m	(30m - 29) – (30m + 30)	60

^a Baseline is the last assessment taken prior to the start of study treatment.

^b Day 1 represents the first day of study treatment.

Please note that telephone visits are not included as only log data will be collected at those visits (e.g. AEs and concomitant medications).

These visit windows will be reviewed and may be updated prior to reporting. Any assessments that fall outside of these windows will be reviewed on a case-by-case basis, and decisions on their handling will be fully documented prior to reporting. Data collected outside these windows will only be listed.

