APPENDIX 1. TIME AND EVENTS SCHEDULES

Event	TIME AND EVENTS SCHEDULE FOR THE STUDY						
	Screening	Baseline ^a	Treatment		Follow-ups		
	Visit 1	Visit 2	Visit 3	Visits 4 & 5	Visits 6+		
Event	Day -28 to 1	Baseline Day 1	Week 2 (\pm 2 day)	Months 1 & 2 (\pm 3 days)	In Clinic at Month 4 and Every 4 Months thereafter until Study Termination Visit ^b (\pm 7 days)	Phone Visits at Month 6 and Every 4 Months thereafter until Study Termination Visit ^b (\pm 3 days)	Study Termination Visit ^c
Informed Consent	X						
Confirmation of eligibility	X	X					
Medical History & Demographics	X						
Physical Examination ^d	X	X		X ^e	X ^f		X ^c
Weight/Height Measurement	X	X ^g			X ^f		X
Vital Signs ^h	X	X	X	X	X ^f		X
Clinical Labs (blood) ⁱ	X	X	X	X	X ^f		X
NT-proBNP (blood) ⁱ	X	X	X	X	X		X
Serum Pregnancy Test for Females ^j	X						
Urine Pregnancy Test for Females ^j		X					
Infectious Disease Screen	X						
6MWT & Functional Class	X	X	X	X	X		X
Pulmonary Function Testing	X						
Inhalation Device User Survey ^k		X	X		X ^f		X
MLWHF questionnaire		X		X ^e	X ^f		X
Patient DPI Training ^l		X	X	X	X		
Record Last Dose of Inhaled Treprostinil		X	X	X	X		X
LIQ861 Administration ^m		X	X	X	X		
Treatment-Emergent Adverse Events ⁿ		X	X	X	X	X	X
Prior Medication Assessment	X	X					
Concomitant Medications		X	X	X	X	X	X
Assess PAH Symptoms		X	X	X	X	X	X
Consider and Record Dose Adjustments			X	X	X	X	
Collect Unused Study Drug			X	X	X		X
Dispense Study Drug			X	X	X ^o		
Schedule Next Visit	X	X	X	X	X ^o	X	

a. This table is for assessments for all subjects not participation in the PK Sub-Study. For Day 1 and Day 2 assessments in the PK Sub-Study see the PK Sub-Study T&E Table (below).

b. Patients will continue on 4-month periodic follow-up visits from the completion of Visit 6 until the Study Termination Visit.

c. Study Termination Visit should be completed within 1 month of drug approval or study termination or when a patient is discontinued from the study.

- d. A full PE will be conducted at Visit 1, at Visit 6 and every 12 months thereafter, and at Study Termination; a brief PE will be conducted during Visit 2 & Visit 5.
- e. Assessment is to be conducted at Visit 5 (Month 2) only.
- f. Assessment is to be conducted at Visit 6 and every 12 months thereafter.
- g. Height does not need to be assessed at Visit 2.

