8.1. ADVERSE EVENTS

AEs will be coded using MedDRA version 20.1.

AEs will be considered TEAE unless there is clear indication that the event occurred prior to the first dose of study drug. AEs present prior to study drug administration that increased in severity or relationship to study drug afterwards will also be classed as TEAEs.

All AEs that occur after the first dose of study drug will be considered to be 'treatment-

'emergent' with the exception of AEs that occur more than 7 days after the last dose of study drug.

Events with missing or partial dates will be handled such that in the absence of contradictory information an AE is treatment emergent (see Section 6.2).

Only TEAEs will be included in the summary tables.

An overall summary will present the number of subjects with:

- any TEAE*
- any TEAE considered as related to study drug (evaluated by the investigator as Related or severity not reported)*
- any serious TEAE*
- any serious TEAE considered as related to study drug*
- Maximum severity TEAEs of mild, moderate or severe; i.e. a subject with TEAEs at different intensities will be summarized at the most severe intensity
- Maximum severity TEAEs considered as related to study drug of mild, moderate or severe; i.e. a subject with TEAEs at different intensities will be summarized at the most severe intensity
- any TEAE leading to study drug discontinuation (i.e. TEAEs reported as having either an action taken as 'Drug Withdrawn') and/or Study Discontinuation*
- any TEAE considered as related study drug discontinuation (i.e. TEAEs reported as having either an action taken as 'Drug Withdrawn') and/or Study Discontinuation *
- any TEAE leading to death*

The table will also include the total number of TEAEs reported for those flagged (*). The total number of unique terms within subjects will also be presented for those flagged (*), counting each TEAE PT only once within each subject.

This overall summary will be presented for both the Safety and mITT populations.

This summary will also be produced using the Safety population for the following:

- the subgroups in Section 6.3
- those TEAEs with an onset up to the Month 2 visit (inclusive) and those with an onset after the Month 2 visit separately.

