8.2. LABORATORY EVALUATIONS

Laboratory safety parameters are to be assessed at Screening, Baseline, Week 2 and Months 1, 2, 4 and every 12 months thereafter.

Observed and change from baseline clinical laboratory data (including hematology and blood chemistry parameters) will be summarized using descriptive statistics, for Months 2 and 4.

A shift from baseline table for Months 2 and 4 will be presented. Normal, abnormal low, abnormal high and missing records will be summarized, with marginal totals, using frequencies and percentages.

In addition to summarizing by visit the last ‘on-treatment’ measurements will also be summarized. The last ‘on-treatment’ measurement must be after Day 1 and within 1 day of the final dose of LIQ861.

All individual laboratory results will be listed. The listing will include change from baseline values and values outside the laboratory reference range will be flagged.

All pregnancy laboratory results (serum and urine) will be listed.

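### Laboratory and vital-sign values from a termination visit held 2 or more days after the last LIQ861 dose enter no summary or shift table, although the endpoint names Early (Study) Termination

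*SAP*

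**What the plan says.** Protocol 3.2.2 gives the safety endpoint as "Changes from Baseline to Month 2/Early Termination in clinical laboratory, physical exam findings, and vital signs". SAP 4.2 restates it as "Changes from Baseline to Month 2/Study Termination in clinical laboratory and vital signs". Its footnote says that changes to Months 2 and 4 will be summarized, and that early-termination data may stand in for a missing visit only if they fall inside the visit window.

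The Study Termination Visit supplies the termination value. Protocol 6.2.6.3 has laboratory tests and vital signs taken there and the time of the last LIQ861 dose recorded; giving LIQ861 is not among its procedures. On timing, Protocol Appendix 1, footnote c, says: "Study Termination Visit should be completed within 1 month of drug approval or study termination or when a patient is discontinued from the study". No interval from the last dose is set.

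SAP 6.4 applies two limits. For most data, "with the exception of laboratory and vital sign data, the visit must be within 7 days of the final dose of study treatment". For the data at issue here, "For laboratory and vital sign data the assessment must be no more than 1 day after the final dose of study treatment". SAP 8.2 and 8.3 tabulate laboratory and vital-sign data at Months 2 and 4 and add a last on-treatment summary, whose value "must be after Day 1 and within 1 day of the final dose of LIQ861". SAP 8.1 counts events after the first dose as treatment-emergent "with the exception of AEs that occur more than 7 days after the last dose of study drug".

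**The concern.** The endpoint has two parts, Month 2 and termination, and the analysis rules leave the second only partly served. A patient who stops at home and attends three days later provides a termination sample that neither the by-visit tables nor the last on-treatment row can use. Patients who stop because of harm may be among those who stop before reaching the clinic. If so, the change-from-Baseline and shift tables lean towards patients who tolerated the drug.

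The SAP gives no reason for 1 day here against 7 days elsewhere. The last on-treatment wording is also ambiguous. Read literally, it leaves the row empty for a patient whose last sample was drawn well before stopping. Scheduled hematology, chemistry and vital signs after Month 4 recur only every 12 months (Protocol 6.2.6.1), so the next are at Month 4 + 12 = Month 16, and a patient stopping between these visits could be such a case.

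**Working it through.** **1. Reproduce the SAP's windows.** Length = last day − first day + 1. Week 2: 22 − 2 + 1 = 21. Month 1: 45 − 23 + 1 = 23. Month 2: 90 − 46 + 1 = 45. Month 4: 150 − 91 + 1 = 60. All match the table in SAP 6.4.

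**2. Trace a termination value.** Let d be the study day of the sample (after Day 1) and g the whole days since the last dose.

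| g | d | Tables it can enter |
|---|---|---|
| 0 or 1 | 46–90 | Month 2; last on-treatment |
| 0 or 1 | 91–150 | Month 4; last on-treatment |
| 0 or 1 | 2–45, or after 150 | Last on-treatment only |
| 2 or more | any | None; listing only |

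The third row arises because Day 2–45 belongs to Week 2 or Month 1, and SAP 8.2 and 8.3 tabulate only Months 2 and 4. The fourth row is the gap.

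**3. Compare the limits.** Laboratory and vital signs: 1 day. Other visit data (SAP 6.4), visit attendance (SAP 7.1) and TEAEs (SAP 8.1): 7 days. A patient can thus count as attending Month 2 under SAP 7.1 while that visit's laboratory values are excluded under SAP 6.4.

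**4. Size visible in the documents.** SAP 3.3 gives 121 enrolled and 113 with a Month 2 visit. 121 − 113 = 8, and 8/121 = 6.6% (exact 95% CI 2.9% to 12.6%). This is neither a count of withdrawals nor an upper bound on values excluded. Some of the 8 may simply have missed the visit (SAP 7.1 has that category), and by step 3 some of the 113 could have excluded values.

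**5. Share of termination values excluded, under an assumption.** The delay is not given. Among patients who stopped at least 1 day before the visit, assume a delay uniform on 1 to G days. Share excluded under the 1-day limit = (G − 1)/G; under a 7-day limit = (G − 7)/G when G exceeds 7, otherwise 0.

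| G (days) | 1-day limit | 7-day limit |
|---|---|---|
| 1 | 0% | 0% |
| 2 | 50% | 0% |
| 3 | 67% | 0% |
| 7 | 86% | 0% |
| 14 | 93% | 50% |
| 30 | 97% | 77% |

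The result runs from 0% to 97% on the assumed delay alone.

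**6. Would a 7-day limit restore the endpoint?** For Month 2 it would add only values with g from 2 to 7 and d from 46 to 90. If termination days before Day 91 were uniform over Day 2–90 (an assumption), 44 of 89 days, or 49%, would fall before Day 46. The window would keep those values out of Month 2 whatever the limit.

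**The case against.** The strongest reply is that little information on harm is lost. Termination samples are collected, and SAP 8.2 and 8.3 list all results with change from Baseline, with out-of-range laboratory values flagged. Protocol 6.5 requires clinically significant laboratory values to be recorded as AEs, and 7.6.5 extends this to clinically relevant vital signs. Such an abnormality arising up to 7 days after the last dose therefore reaches the TEAE tables. That stands. What is missing is the numerical contribution to means and shift cells, and beyond 7 days the TEAE route closes too.

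A 1-day limit is also a coherent on-treatment definition for a drug given four times daily. On its natural reading, the last on-treatment row takes a dropout's last on-drug value, such as Week 2 or Month 1. Both points stand. They justify keeping that analysis, but it does not deliver a termination value.

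Attrition is partly visible: SAP 6.2.5 gives categorical summaries a category for earlier withdrawal. For continuous data, however, the same section leaves earlier discontinuations out of the missing count.

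SAP 6.4 provides case-by-case review of assessments outside the windows, but then says that such data will only be listed.

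The long interval after Month 4 comes from the protocol's schedule, not from the 1-day rule, and unscheduled tests are allowed (Protocol 6.3).

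**Conclusion.** The gap is real but bounded. The endpoint names termination, the termination visit is not tied to the last dose, and every laboratory or vital-sign value taken 2 or more days after the last dose is confined to listings. The window rule in the SAP 4.2 footnote separately keeps termination values before Day 46 out of Month 2.

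A reader might infer more than the documents support:

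- That most termination values are lost. This cannot be derived without the delays from last dose to visit; a visit on the last-dose day or the next day is kept.
- That dropouts are not measured. They are measured and listed, their values can enter the last on-treatment row, and their clinically significant abnormalities can be TEAEs.
- That the 8 of 121 are dropouts whose endpoint is lost. SAP 3.3 says only that they had no Month 2 visit.
- That moving the limit to 7 days would restore the endpoint. The visit window would still exclude early values, and the choice of limit is debatable.

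The number of values affected, and the direction of any bias, remain unknown. The suggestion that the tables favour patients who tolerated the drug assumes that those stopping for harm tend to attend 2 or more days later. Because the endpoint is descriptive, no test or error rate is affected.

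**What to change.** In SAP 8.2 and 8.3, add a summary row titled 'Early Termination / last post-Baseline value', with a matching shift table for laboratory data. It should include the Study Termination Visit regardless of time since last dose or visit window, split as 1 day or less, 2–7 days, and more than 7 days since the last dose. Report how many values the 1-day rule and the visit window each exclude.

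Reword the last on-treatment rule in both sections as: the last value after Day 1 and no later than 1 day after the final dose. Keep that analysis, and leave the 1-day limit in SAP 6.4 unchanged.

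The cost is SAP wording, the added rows and one shift table, all from data already collected; SAP section 2 allows amendment before database lock. The downside is that some values in the new row are off drug, which the split makes visible.
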